Appendix A

Instructions for Patients Assigned to the Incentive Spirometer

Thank you for participating in the GO² PEEP research study. You have been assigned to the study group using the incentive spirometer.

1. To use the incentive spirometer, sit up as far as you can in bed and hold the incentive spirometer
2. Take a deep breath in and then blow out all the way through your mouth with pursed lips.
3. Put the mouthpiece in your mouth. Seal your lips tightly around it.
4. **Breathe in slowly through your mouth as deep as possible.** The blue disc will rise toward the top of the column.
5. Keep the blue indicator on the right side between the arrows.
6. Open your mouth and then breathe out, allowing the blue disc to fall to the bottom of the column.
7. Rest for a few seconds and repeat steps above at least 10 times every hour while you are awake. If you feel dizzy, slow your breathing down.
8. Move the arrow on the left side of the spirometer to show the highest number you reached.
9. After each set of 10 deep breaths, practice coughing to be sure your lungs are clear. You may use the device additionally if desired.
10. Place a pillow firmly against incision area to ease any discomfort while coughing.

Practice this 4-6 times each day before your surgery.

If there are any issues or problems contact [name] or the research coordinator at [contact] as soon as possible.

Instructions for Patients Assigned to the Bidirectional Oxygenation Mouthpiece

Thank you for participating in the GO² PEEP research study. You have been assigned to the study group using the bidirectional oxygenation mouthpiece.

1. To use mouth piece, place the device inside the mouth, loosely biting down on the bite plate. Allow your lips to surround the lip flange.
2. Breathe in as deeply as you can in a steady manner. Exhale through the device as completely and forcibly as possible.
3. Repeat the process, breathing as deeply as possible and exhaling for 2.5 minutes, rest for 10 minutes and then repeat another 2.5 minutes. Complete this every hour while awake.
4. After using mouth piece each hour, practice coughing to be sure your lungs are clear. You may use the device additionally if desired.
5. Place a pillow firmly against incision area to ease any discomfort while coughing.

Practice this 4-6 times each day before your surgery.

If there are any issues or problems contact [name] or the research coordinator at [contact] as soon as possible.

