1. Atelectasis on CXR (Atelectasis Severity Score) immediately post-op and on postoperative days 1-4
2. Oxygen requirement 1, 6, 12 and 24 hours post-extubation and daily each morning
3. CO₂ level at 1, 6, 12 and 24 hours post-extubation
4. FEV1 and FVC measurements pre-op and on postoperative day 3
5. Respiratory rate 1, 6, 12 and 24 hours post-extubation then daily each morning
6. Peak body temperature every 24 hours (as a marker of atelectasis)

Study Procedures

After an eligible patient has provided written informed consent, he/she will be randomly assigned to one of two study cohorts: incentive spirometer (Control Arm) or Bidirectional Oxygenation Valve (G02 Mouthpiece).

Permuted block randomization will be employed to ensure balance between groups when the number of recruited patients reaches a multiple of the block size. All patients will undergo additional postoperative respiratory therapy, including: deep breathing exercises, directed cough, early mobilization and optimal analgesia per routine care. Mouthpieces for each study arm will be provided to a patient throughout the hospitalization.

Both cohorts will use the assigned device following similar protocols:

1. Proper positioning of the patient in bed.
2. Proper positioning of the incentive spirometer or Go2 mouthpiece.
3. A breath cycle will consist of 10 breaths every hour while awake. See instructions in Appendix A.
4. The research assistant will provide adequate training for both devices and will supervise their use.

Arterial blood gases (ABGs) will be collected on 2L/NC (x 5 min) at 1, 6, 12 and 24 post-extubation (+/- 1 hour). Pt. will be asked to use assigned device (incentive spirometer or GO2 mouthpiece) before each ABG is collected. Blood samples will be tested locally at the Emory St. Joseph's Hospital Laboratory.

A chest radiograph will be obtained immediately post-op and daily on post-op days 1-4 to assess the presence of atelectasis using the atelectasis severity score. X-rays will be read by a single radiologist in a blinded fashion.

Respiratory rate will be measured 1, 6, 12 and 24 hours post-extubation then daily each morning.

Body temperature will be measured per nursing routine (as a marker of atelectasis). Temperature max will be recorded each 24 hours.

Schedule of Assessments

Study Procedures	Baseline (up to 30 days before surgery)	Post-Op	POD 1	POD2	POD3	POD4
Consent	X					
Pulmonary function test (PFT)	X				X ²	
Randomization	X					

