Treatment: breathing exercises with mouthpieces		X	X	X	X	X
Arterial blood gas (ABGs)			X ¹	X ¹		
Chest x-ray with Atelectasis Severity Score	X	X	X	X	X	X
RR and body temp		X	X	X	X	X
Peak Body Temp			X	X	X	X
Adverse Events		X	X	X	X	X
Use of Device Questionnaire						X ³

¹ABGs 1, 6, 12 and 24 post extubation.

²Performed for research purposes only

³Can be done from POD4 up until discharge from hospital

Statistical Analysis Plan

As a pilot study, our goal is to examine the feasibility and safety of conducting this pilot study on a larger scale. We evaluate the feasibility of recruitment, retention, assessment and implementation of the proposed interventions. We wish to identify any potential flaws in the study design and potential challenges in the subsequent large-scale study. Moreover, the pilot data will give us a first impression of the variability and effect sizes of PaO₂ in the patient population of interest and thus assist in the sample

size and power calculation of the subsequent larger study. Finally, the data that we collect from this pilot will help identify modifications needed in the planning and design of the subsequent study.

We will also assess safety of the new mouthpiece with close monitoring of patient symptoms, physical exam, PaO₂, PCO₂, CXR results, vital signs, and temperature. At the conclusion of the study, we will attempt to assess between-group differences, but given that low power is characteristic of pilot studies, statistical significance is not the focus of the analysis. However, we plan to provide statistical summaries that would be useful in the subsequent study and to other researchers, such as number of patients screened per month, number of patients enrolled per month, proportion of screen eligible who enrolled, lost-to-follow rate, study costs.

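### Appendix A tells spirometer patients to slow their breathing if dizzy, but the mouthpiece sheet gives no such advice (minor patient-safety point)

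*Combined protocol and SAP*

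**What the plan says.** Study Procedures, item 3, refers both cohorts to Appendix A, which prints one instruction sheet per arm.

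- **Spirometer sheet.** Item 2 asks the patient to "blow out all the way through your mouth with pursed lips", and item 4 asks for a slow inhalation of maximal depth. Item 7 asks for a short rest between breaths and at least ten repeats per waking hour, and adds "If you feel dizzy, slow your breathing down".
- **Mouthpiece sheet.** Item 2 asks for a deep, steady inhalation and then "Exhale through the device as completely and forcibly as possible". Item 3 sets the pattern for each waking hour: "breathing as deeply as possible and exhaling for 2.5 minutes, rest for 10 minutes and then repeat another 2.5 minutes". Neither items 1 to 5 nor the closing lines mention dizziness, slowing down or stopping.
- **Both sheets.** Each ends with "Practice this 4-6 times each day before your surgery" and a contact line that begins "If there are any issues or problems contact".

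Elsewhere, General Design Limitations names hyperventilation or respiratory alkalosis in connection with subjects opting out, and lists unsupervised device use as a pitfall. Study Procedures has a research assistant train patients on both devices and supervise use. The Statistical Analysis Plan names symptoms, physical examination, PaO₂, PCO₂, chest X-ray, vital signs and temperature as safety monitoring for the mouthpiece.

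**The concern.** Prolonged deep breathing can cause dizziness through hyperventilation, and the protocol itself foresees hyperventilation. The authors thought the spirometer sheet needed a sentence on this. The investigational arm's sheet, which asks for sustained and forcible breathing, lacks it, and no device-related reason is given.

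The sheet is what the patient has in hand when no staff member is present, possibly including the pre-operative practice that both sheets request. A dizzy patient who follows the mouthpiece sheet as written finds no prompt to ease off. At stake is patient comfort and safety in a pilot whose stated objective is feasibility and safety. Inference is not at stake.

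**Working it through.** The plan has no figure to reproduce here. The check is a comparison of the two sheets, followed by a search of the rest of the document for equivalent advice.

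**1. The two sheets side by side**

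| Item | Spirometer sheet | Mouthpiece sheet |
|---|---|---|
| Effort | Full exhalation, maximal slow inhalation | Maximal inhalation, complete forcible exhalation |
| Amount per waking hour | At least 10 breaths | 2 × 2.5 min = 5 min |
| Pacing | Slow inhalation, indicator kept in range, a few seconds' rest between breaths | Steady inhalation, 10 minutes' rest between bouts |
| Dizziness advice | 1 instruction (item 7) | 0 |
| General contact line | Yes | Yes |

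Both sheets ask for near-maximal effort, so the difference of interest is the missing advice. The mouthpiece sheet appears complete, with only contact details removed.

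**2. Which breathing amount applies.** Study Procedures, item 3, sets ten breaths per waking hour for both cohorts and then refers to Appendix A, where the mouthpiece sheet says 5 minutes. The documents do not settle which governs. If the sheet is followed, and assuming 6 to 12 deep breaths per minute (a rate not in the documents), the amount is 5 × 6 = 30 to 5 × 12 = 60 breaths per hour, or 3 to 6 times the spirometer minimum of 10. If item 3 is followed, the two amounts are equal. The advice is missing in either case.

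**3. Patients affected.** The planned sample is 20. The allocation ratio is not stated. At 1:1, 20 / 2 = 10 patients would receive the sheet without the advice.

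**4. What else might cover dizziness**

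- *Training and supervision* (Study Procedures, item 4): both arms, content not described. General Design Limitations concedes that use may be unsupervised.
- *Safety monitoring* (Statistical Analysis Plan): symptoms, PCO₂ and vital signs are named. CO₂ is also a secondary endpoint, from blood gases at 1, 6, 12 and 24 hours after extubation, four in all.
- *Respiratory rate*: "Respiratory rate will be measured 1, 6, 12 and 24 hours post-extubation then daily each morning". The schedule row runs to POD4.
- *Adverse Events list*: five items, none of which is dizziness or a fall in CO₂. The second item, read as CO₂, concerns a rise. This count has to be read with the wider monitoring above.
- *"Use of Device Questionnaire"*: from POD4 to discharge, content not in our copy.

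These may detect a problem. None is stated to tell the patient what to do when dizzy.

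**The case against.** The strongest reply is that this is one sentence of leaflet wording with no bearing on design or analysis, and that patients may get the advice anyway. Training covers both devices, the consent form is not in our copy, and the mouthpiece sheet has partial safeguards: steady inhalation, a built-in rest and a contact line. Most of this stands. It limits the point to the written sheets and keeps it minor. It does not remove the point: no text that we can see gives mouthpiece patients the advice, and the contact line is on the spirometer sheet too, where the authors still added the specific sentence.

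A reader might infer three stronger claims, which the documents do not support.

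- *That hyperventilation is unmonitored in the mouthpiece arm, because none of the five listed adverse events covers it.* The Statistical Analysis Plan names symptoms, PCO₂ and vital signs as safety monitoring for this device.
- *That mouthpiece patients breathe several times as much as spirometer patients.* Study Procedures sets the same ten breaths for both arms, and the 3-to-6-fold figure rests on an assumed breathing rate.
- *That the protocol expects hyperventilation mainly with the mouthpiece.* General Design Limitations does not tie it to one arm. The pitfall about the assigned mouthpiece can mean either device, since Study Procedures uses the word for both arms.

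**Conclusion.** The point holds as a minor patient-safety improvement. One sheet has the dizziness advice and the other does not, and the protocol foresees the hazard without limiting it to one arm. Confidence is high for the difference in the text. Whether any patient actually goes without the advice cannot be judged from the documents, and neither can the frequency of dizziness. The figure of about 10 patients assumes 1:1 allocation of 20. No endpoint, sample size, error rate or analysis changes.

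**What to change.** Add to item 3 of the mouthpiece sheet an instruction to slow the breathing or pause if dizzy, matching the spirometer sheet. Have the research assistant give the same advice to both arms during training. The cost is a one-sentence revision through the IRB. The downside is that mouthpiece patients may pause more often, so slightly less device use may be delivered.

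I would not ask for a record of each session slowed or stopped for dizziness. Assuming 12 to 16 waking hours a day over 4 days, there are 12 × 4 = 48 to 16 × 4 = 64 hourly prompts per patient, before any pre-operative practice. Counting slowed or stopped sessions would need a diary, which is out of proportion to the point.

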Funding for the study will be provided by PEEP Medical, LLC. Bidirectional oxygenation mouthpieces will be provided by the Sponsor. Incentive spirometers will be provided by the hospital as part of the routine postoperative respiratory therapy.

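### Both arms are told to practise with the assigned device before surgery, but the only stated adverse event window opens after it

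*Combined protocol and SAP*

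**What the plan says.** Appendix A gives each arm its own instruction sheet, and both end with the same line: "Practice this 4-6 times each day before your surgery". The mouthpiece sheet asks for forceful effort: "Exhale through the device as completely and forcibly as possible". The spirometer sheet foresees a symptom: "If you feel dizzy, slow your breathing down". The mouthpiece sheet has no such line.

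In the Schedule of Assessments, Consent and Randomization are marked under Baseline, a period of up to 30 days ahead of the operation. The row "Treatment: breathing exercises with mouthpieces" and the Adverse Events row are both empty at Baseline and marked from Post-Op to POD4.

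The Adverse Events section lists five events (hypoxia, a CO rise, increasing oxygen requirement, reintubation, pneumothorax) and gives no start date. Serious events are reported under IRB policy, again with no stated window. The Statistical Analysis Plan states: "We will also assess safety of the new mouthpiece with close monitoring of patient symptoms".

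On supply, Study Procedures says "Mouthpieces for each study arm will be provided to a patient throughout the hospitalization", and Funding Source says "Incentive spirometers will be provided by the hospital as part of the routine postoperative respiratory therapy". No section gives the date on which a patient receives the device.

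**The concern.** The Study Objective names safety alongside feasibility. If the sheets are followed, a cardiac surgical patient's first use of the investigational valve comes before surgery, possibly at home. The Schedule places no treatment record and no adverse event assessment there. A patient who became dizzy, short of breath or uncomfortable, or who stopped using the device, would be counted only if he or she chose to report it.

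Pre-operative events would also be the easier ones to interpret, because anaesthesia, incision and analgesia are not yet competing explanations. The General Design Limitations section itself mentions unsupervised use, and it names hyperventilation and respiratory alkalosis among possible reasons for opting out. At stake is whether the pilot's safety summary covers all the device use that the plan directs.

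**Working it through.** The plan gives no figure for pre-operative exposure, so there is none to reproduce. The check sets the texts side by side and then brackets the amount of use.

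**Timing, item by item**

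| Item | Source | Before surgery | Post-Op to POD4 |
|---|---|---|---|
| Device known to patient and staff | Schedule, Randomization row | yes | yes |
| Device use directed | Appendix A, both sheets | yes, 4–6 times a day | yes, hourly while awake |
| Treatment recorded | Schedule, Treatment row | blank | marked |
| Adverse events assessed | Schedule, Adverse Events row | blank | marked |
| Start date for the five listed events | Adverse Events section | none stated | none stated |

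Only the Schedule gives a timing for adverse event assessment, and it begins after the directed practice.

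**Amount of use**

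Sessions before surgery = days the device is held before surgery × 4 to 6 a day. The number of days is not in the documents, so three cases are shown:

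- Device issued only after surgery: 0 × (4 to 6) = 0 sessions.
- One day of practice, an assumption suggested by the consent section's aim of starting at least 24 hours ahead when possible: 1 × 4 = 4 to 1 × 6 = 6 sessions.
- Device issued at randomization, at the outer limit of the Baseline window, and used every day: 30 × 4 = 120 to 30 × 6 = 180 sessions.

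In the mouthpiece arm, if one practice means the full hourly routine (an assumption), a session is 2 × 2.5 = 5 minutes of breathing through the valve. That gives 4 × 5 = 20 to 6 × 5 = 30 minutes a day. Over 30 days it is 30 × 20 = 600 to 30 × 30 = 900 minutes, or 10 to 15 hours. It is less if practice means only rehearsing the technique.

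The bracket runs from 0 to 180 sessions per patient. These are bounds on use, not an estimate of it, and they say nothing about risk.

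**What could be missed**

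Of the five listed events, reintubation cannot arise from pre-operative practice. A pneumothorax or a rising oxygen requirement would normally come to medical attention. Hypoxia and a CO rise need a measurement. None of the five is a symptom, although the Statistical Analysis Plan promises to follow symptoms. What remains is mainly the non-serious event that the patient does not volunteer.

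**The case against.** The strongest reply is that the exposure may not exist. Mouthpiece supply is tied to the hospital stay, spirometer supply to postoperative care, and the Treatment row starts at Post-Op. If devices are handed out only after surgery, the practice line has no effect. That stands as a possibility and is why the bracket begins at zero. It does not remove the mismatch: the instruction then cannot be followed and should be deleted.

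Second, a mark in the Schedule shows when an assessment takes place, not how far back it looks. The first post-operative check could ask about events since first use. The text does not say so, and the gap can be closed by saying it.

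Third, there are backstops. SAE reporting has no time limit, both sheets give a contact, and the eligibility criteria exclude patients with prior pneumothorax, emphysema or FEV1 below 75% predicted. A Baseline chest film is scheduled, though its timing relative to practice is not given. The plan also says "The research assistant will provide adequate training for both devices and will supervise their use", without saying when. The data collection forms and the device questionnaire are not shown and may already ask. These points shrink the gap. The contact line depends on the patient, however, and the questionnaire is not given until POD4 or later.

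A reader might infer that one missed event would shift an arm's adverse event rate appreciably in a trial of 20 patients. The documents do not support that. An unreported dizzy spell is not among the five listed events and would not count towards their rate even on POD2, and no event rate is given. Nor do they support the inference that patients will practise unmonitored for 30 days, since no issue date is stated. Equally, the 24-hour consent lead time does not cap exposure at one day, because the Baseline window is far longer.

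**Conclusion.** The point holds as a minor one. As written, the plan directs device use in both arms before surgery and states an adverse event window that begins only afterwards, while safety is a study objective. The size of the gap is not established: 0 sessions if issue is post-operative, 4 to 6 for one day, and 120 to 180 at most under issue 30 days ahead with daily practice. It is confined mainly to non-serious, unvolunteered events, and no effect on event rates can be quantified. The conclusion rests on the Schedule being the only stated timing, and on the unseen forms not already asking about the practice period.

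**What to change.** Start the Treatment and Adverse Events rows at first device use in both arms. Record the device issue date for each patient. At admission for surgery, ask each patient about symptoms during practice (dizziness, dyspnoea, chest pain, stopping use) and about any diagnosed pneumothorax. Report pre-operative events separately from post-operative ones. If no pre-operative use is intended, delete the practice line from both sheets instead.

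The cost is one Schedule amendment, one date field and one question. The answers rest on recall and cannot recover saturation values, so the hypoxia criterion would remain unmeasured before surgery.
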